17.0 Provisions to Protect the Privacy Interests of Participants

17.1 Steps to protect participants' privacy interests. If any of the following apply, check the box for convenience:

- Procedures will be performed in a private area where others cannot see the procedures being performed or overhear the conversation between subjects and researchers.
- All members of the study team are up to date on their institutional HIPAA training.
- The study is not collecting information that could pose legal or reputational risks to participants.

Almost all study activities (apart from biochemical verification visits) will occur by phone. To protect participant privacy, study coordinators will encourage participants to move to private spaces during recruitment and study calls, and will offer to reschedule calls if participants are unable to do so.

Biochemical verification tests will happen in private spaces, as well (CO tests will be conducted in private rooms and urine samples will be self-collected by participants in private restrooms, without staff observation).

17.2 Sensitive information.

The only sensitive information to be collected in the study is self-reported use of cannabis. This information is needed to assess concurrent use of cannabis that may influence smoking cessation success and to interpret carbon monoxide and cotinine tests that

PROTOCOL TITLE: Comparative Effectiveness Trial of Tobacco Cessation Treatments among Cancer Patients who Smoke

could be influenced by use of combustible cannabis (in the case of CO) and use of cannabis in tobacco leaf wrappers (in the case of CO and cotinine).

17.3 Steps to make the participants feel at ease.

Collection of sensitive information about subjects will be limited to the amount necessary to achieve the aims of the research and to interpret biochemically verified abstinence data correctly.

Participants will be informed that they have the right to decline to answer any question they prefer not to answer, without penalty or punishment, and that the study has a Certificate of Confidentiality.

17.4 Authorized access to UW Health records.

UW Health records will be accessed to identify patients eligible for tobacco treatment outreach by the UW-CTRI team only with authorization from UW Health. UW Health EHR and Cancer Registry data of identified potentially eligible patients who did not actively decline study participation will be extracted and de-identified to examine the representativeness of the patients who enrolled in the CET. A list of the specific data elements is available in a protocol supplement document.

In the CET, participants will provide informed consent for UW-CTRI study coordinators to coordinate care with their care teams in Health Link (i.e., to give providers an opportunity to review and disapprove study medications prior to their dispensing, and to update patient medication lists to reflect study medications dispensed). This will be covered during the informed consent process. UW Health records of CET participants will be accessed and EHR data and Cancer Registry data will be extracted to examine preliminary treatment utilization, complications, clinical outcomes, and cost-effectiveness. A list of the specific data elements is available in a protocol supplement document.

18.0 Sharing of Results

18.1 Result sharing with participants or others.

The only results that will be shared with participants will be CO test results, as these results are available immediately upon testing. Study coordinators collecting CO samples will congratulate patients whose CO tests indicate abstinence from combustible products, and will explore sources of exposure to CO (e.g., passive smoke exposure, car exhaust, improperly vented or malfunctioning equipment) among those whose expired breath contains more than 5 parts per million CO. Urine cotinine and salivary cotinine testing results will not be

PROTOCOL TITLE: Comparative Effectiveness Trial of Tobacco Cessation Treatments among Cancer Patients who Smoke

available immediately (urine testing takes at least 15 minutes, saliva samples need to be shipped for testing). These results will not be captured in participants' health records, as they capture abstinence at a particular time (in the past 1-2 days for CO, and in the past 1-2 weeks for cotinine), and should not be used to influence ongoing healthcare.

18.2 Plans to share study results with the public.

Aggregate results from this research will be shared with the scientific community and our research collaborators. The findings from this research will also be shared upon request with study participants.

19.0 Data and Specimen Banking

19.1 Data and/or specimens banking for future use. No study specimens will be banked for future uses outside of the currently described protocol. Study data and records will be de-identified and archived per record retention policy. Fully deidentified/anonymized data will be stored for 7 years in case replication, follow-up, or sensitivity analyses are necessary.

19.2 Data to be stored. Data to be stored for additional analyses consistent with the original study purpose described to participants will be fully deidentified and anonymized and will include EHR-derived data on smoking status, demographics (in broad categories), and REDCap data on smoking cessation treatment utilization, experiences, and abstinence. Data from qualitative interviews will be anonymized transcripts and thematic codes and sample quotes.

19.3 Procedures to release data. Data will only be shared under the auspices of an approved and executed Data Use Agreement, in accordance with university regulations.

19.4 Participant withdrawal of banked data/specimens from future research use. CET participants will not be able to withdraw data from the repository, as it will be fully anonymized and it will no longer be possible to withdraw data from a particular individual due to the lack of identifiers in the data.

20.0 Study Analysis

20.1 Statistical Hypotheses.

The primary hypothesis to be tested for Aim 1 is that at least 12% of eligible adult patients who have cancer and smoke cigarettes and are referred to the tobacco treatment outreach team will initiate an

PROTOCOL TITLE: Comparative Effectiveness Trial of Tobacco Cessation Treatments among Cancer Patients who Smoke

evidence-based form of smoking treatment (either Wisconsin Tobacco Quit Line care or treatment offered in the CET).

The primary hypothesis to be tested for Aim 2 is that more-intensive, cancer-specific smoking cessation treatment will increase the log odds of achieving 7-day abstinence 6 months after a target quit date by at least 50% over the comparator condition (predicted odds ratio ≥ 1.50 in this superiority comparison).

Secondary hypotheses include the following:

For Aim 3, we hypothesize that the majority ($\geq 50\%$) of patients assigned to each condition will initiate treatment and will receive at least some counseling and use at least some of the provided medication. We expect retention, adherence, and satisfaction with treatment to be higher in the enhanced treatment relative to standard care. We anticipate that the more intensive, enhanced treatment, although more costly, will be cost-effective in terms of the incremental cost effectiveness ratio per additional patient who quits smoking, relative to the comparator condition and to other preventive health interventions. For these superiority hypotheses, the null hypotheses are that the two treatments are equally acceptable and efficient.

For Aim 4, we expect to elicit information that will help us better communicate with and support patients eligible for tobacco treatment outreach and CET counseling by learning more about the experiences and perspectives of people who have had cancer.

For Aim 5, we expect treatment reach to be especially high among historically undertreated populations (including African-American, Medicaid-eligible patients, and those from disadvantaged neighborhoods), and for the effects of enhanced treatment (vs. standard care) to be similar across patient subgroups. Thus, we are anticipating superior reach in historically underserved patient groups, and equivalent effectiveness across patient groups.

20.2 Sample Size Justification.

In this pilot study, we seek to demonstrate the feasibility and acceptability of the proactive outreach model as a way to enhance the reach of smoking treatment, and as a feasible way to recruit participants for a CET of enhanced vs. standard smoking cessation treatment. We also hope to generate estimates of enhanced vs. standard treatment effects on biochemically verified 7-day point-prevalence abstinence rates 6 months after a target quit date (primary outcome) and other abstinence measures (e.g., self-reported prolonged and point-prevalence abstinence 3 and 6 months post-quit). As such, we selected a sample size of 50 to generate stable estimates of the size of treatment effects on these outcomes and costs,

PROTOCOL TITLE: Comparative Effectiveness Trial of Tobacco Cessation Treatments among Cancer Patients who Smoke

and to permit exploration of differences in treatment effects by sex, race, ethnicity, and disadvantage. A sample of 50, while too small to sensitively test for moderate treatment benefits, is sufficient to pilot test all study and treatment procedures and to yield informative effect estimates that will guide a future, full-scale CET of standard and enhanced care.

The primary outcome will be analyzed in an intent-to-treat analysis in which all randomized participants are included, and missing cases are assumed to be non-abstinent. This will be supplemented by sensitivity analyses that again use the full sample of randomized participants to examine robustness of results across different assumptions regarding missingness. Multiple imputation will not be used in this pilot project.

For the qualitative study, we will recruit as many participants as we can until we reach thematic saturation in qualitative data coding. We anticipate that this will occur with fewer than 32 participants.

20.3 Participant Population(s) for Analysis.

We will examine reach of the treatment by computing the proportion of all participants meeting inclusion criteria for proactive tobacco outreach who were referred to WTQL, referred to their PCP, and the proportion who were screened for, eligible for, and enrolled/randomized in the CET. As such, the pool of participants for Aim 1 includes everyone eligible for inclusion on at least 1 CRDS report that guides proactive tobacco treatment outreach. The pool of participants included in Aims 2, 3 and 5 will comprise all participants who were randomized to treatment in the CET. The pool for Aim 4 will include all participants who participated in a qualitative interview.

20.4 Statistical Methods.

Descriptive statistics will be used to characterize smoking treatment reach (the proportion of eligible patients who initiate any smoking cessation treatment, and the proportion who enroll in the CET. These rates will be computed overall, and by patient subpopulation.

Logistic regression will be used to estimate the effects of treatment condition on binary outcome data (e.g., abstinence, side effects), overall and by patient subgroups (i.e., moderation effects). Odds ratios and numbers needed to treat will be computed to estimate treatment effect sizes.

Analyses of variance will be used to examine condition effects on continuous variables such as ratings of treatment satisfaction, burden, and treatment effects on ratings of patient experiences and candidate treatment mediators (e.g., withdrawal). Treatment effect sizes will be computed. Cost-effectiveness will be calculated based on the incremental cost-effectiveness

PROTOCOL TITLE: Comparative Effectiveness Trial of Tobacco Cessation Treatments among Cancer Patients who Smoke

ratio of enhanced treatment versus standard treatment per each additional case of abstinence.

Thematic analysis of qualitative interview will identify themes that emerge in patient interviews in the following areas: cancer experiences, supportive care outreach, tobacco history, and tobacco treatment.

20.5 Planned Interim Analysis.

No formal inferential interim analyses are planned for this pilot study, but safety data will be examined on an on-going basis to determine if individual participants are at risk or if any treatment element or condition is exerting an iatrogenic effect. If any meaningful evidence of this is detected the DSMC will be consulted along with the IRB to consider study discontinuation or changes. If any danger is deemed likely and significant the study will be immediately suspended.

20.6 Handling of Missing Data. The intent-to-treat principle will be applied to primary analyses. Patients who do not initiate smoking treatment via a UW-CTRI study coordinator will be assumed to not have initiated treatment. In analyses of abstinence, cases who do not report abstinence and provide biochemical evidence of abstinence will be coded as still smoking in primary analyses. This will be supplemented by sensitivity analyses to estimate treatment effects under different assumptions regarding missing data (e.g., if 10%, 20% or 30% of people without verified abstinence are abstinent).

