4. Differences in rates of treatment reach, retention, and completion by patient factors (demographics, nicotine dependence, smoking history). (Aim 5).
5. Moderation of treatment effects (high- vs. low-intensity) by patient factors. (Aim 5).

PROTOCOL TITLE: Comparative Effectiveness Trial of Tobacco Cessation Treatments among Cancer Patients who Smoke

6. Health outcomes (e.g., cancer mortality, cancer progression, new cancer diagnoses, treatment side effects).

3.5 Primary safety endpoints.

1. Adverse events, by treatment condition.
2. Serious adverse events, by treatment condition.

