4.0 Number of Participants

4.1 Total number of participants to be accrued. Up to 82 adult participants will be enrolled in the clinical trial by UW-CTRI staff from UW Carbon Cancer Center clinic referrals over 12-30 months. We will continue enrolling within each clinic until we reach saturation in qualitative data analysis of patient interviews (maximum N=32) and until we reach our target enrollment for the CET (N=50).

4.2 Number of participants needed to complete the research procedures. We anticipate that we will engage 12% of participants in some form of evidence-based treatment, and that 50 will enroll in the proposed comparative effectiveness study while another 50 will opt for the Wisconsin Tobacco Quit Line. As such, we anticipate that we will need to reach out to approximately 833 patients who meet criteria to be included on the quarterly CRDS reports that will guide proactive outreach letters and calls. We anticipate that the remaining 733 participants will either opt-out of smoking treatment outreach, will not be reached by the outreach team, will decline tobacco treatment, will elect to pursue treatment via their primary care provider or other means (e.g., over-the-counter) rather than to use formal treatment, or will not complete the treatment enrollment process for other reasons.

Among the 50 participants who enroll in the CET, we will use an intent-to-treat approach to data analyses so that all randomized participants will be included in key analyses of feasibility, acceptability, and abstinence rates, even if lost to follow-up. In primary analyses of abstinence outcomes, missing cases will be treated as still smoking. This will be supplemented by sensitivity analyses under varying assumptions regarding censored data (i.e., that 5%, 10%, or 20% of missing data are abstinent).

For the qualitative interviews, even 2-5 interviews could inform and enhance study methods. We anticipate that we could reach thematic saturation in qualitative data coding with fewer than 32 interviews, and have set 32 as an upper limit for recruitment.

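### The Aim 5 hypothesis of superior reach has no planned contrast or interval, and its stated analysis pool holds only patients who have already been reached

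*Combined protocol and SAP*

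**What the plan says.** Section 20.1 closes its Aim 5 paragraph with "Thus, we are anticipating superior reach in historically underserved patient groups", paired with an expectation that effectiveness will be the same in all groups. The groups are given as "including African-American, Medicaid-eligible patients, and those from disadvantaged neighborhoods". Exploratory endpoint 4 in section 3.4 is the matching quantity: "Differences in rates of treatment reach, retention, and completion by patient factors".

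For the analysis, section 20.4 states "Descriptive statistics will be used to characterize smoking treatment reach" and then "These rates will be computed overall, and by patient subpopulation". The only regression for binary outcomes concerns the randomized arms: "Logistic regression will be used to estimate the effects of treatment condition on binary outcome data (e.g., abstinence, side effects".

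Section 20.3 defines the Aim 1 pool as every patient who qualifies for at least one of the quarterly health-record (CRDS) reports that drive outreach. It defines the pool for Aims 2, 3 and 5 as the participants randomized in the comparative effectiveness trial (CET).

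The status of the hypothesis varies. Section 3.3 lists it as exploratory, section 20.1 as secondary. Section 3.1 says the endpoints serve to generate estimates for a later full-scale trial.

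**The concern.** Two gaps meet on the same hypothesis.

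- **Method.** A claim that one group's reach exceeds another's needs a difference or ratio and a measure of its uncertainty. Section 20.4 supplies neither for reach. The logistic regression does not fill the gap, because reach is settled before anyone is randomized and so is not an effect of treatment condition.
- **Population.** Section 20.3 sends Aim 5 to a pool in which everyone has started treatment. Reach does not vary there.

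Equity of reach is also a reason the protocol gives, in sections 8.3 and 13.4, for extracting record data on patients who never consented to the trial. If only raw subgroup percentages are reported, a gap of a few points in a small group may be read as a finding in either direction, and nothing on the page would show how much of it chance could explain.

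**Working it through.** **1. The plan's own denominator.** Section 4.2 says "We anticipate that we will engage 12% of participants in some form of evidence-based treatment", with 50 patients in the trial and 50 on the quit line. (50 + 50)/0.12 = 833.3, and 833 − 100 = 733. Both match the stated 833 and 733.

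**2. Reach in the pool that section 20.3 assigns.** Of 50 randomized participants, 50 count as reached. Reach is 100% in every subgroup, so every subgroup difference is zero by construction. The 50 quit-line users are also absent, although section 20.1 counts them as reached. In the Aim 1 pool the expected figure is 100/833 = 12%, and subgroup differences can be estimated.

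**3. Precision in the Aim 1 pool.** The documents give no subgroup sizes, so n₁ is assumed and n₀ = 833 − n₁. Half-width = 1.96 × √[0.12 × 0.88 × (1/n₁ + 1/n₀)].

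| Assumed n₁ | Share of 833 | 95% half-width |
|---|---|---|
| 25 | 3% | 12.9 points |
| 42 | 5% | 10.1 points |
| 83 | 10% | 7.4 points |
| 167 | 20% | 5.5 points |
| 208 | 25% | 5.1 points |

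For n₁ = 83: 1.96 × √[0.1056 × (1/83 + 1/750)] = 1.96 × 0.0376 = 0.074.

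**4. What bare percentages would show with no true difference.** This step needs a reading rule that the documents do not contain. Two are shown: any one of the three groups higher than its complement, and all three higher. If each contrast has an even chance of being positive and each pair correlates at ρ, then P(all three higher) = 1/8 + 3·arcsin(ρ)/(4π), and by symmetry P(any higher) = 1 − P(all three higher). At ρ = 0 these are 12.5% and 87.5%. At ρ = 0.5 they are 25.0% and 75.0%.

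Simulation: N = 833, 12% reach in every group, assumed shares of 8, 15 and 20%, overlap set by a latent correlation r between memberships, 20,000 runs per row.

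| Latent r | Any of three higher | All three higher |
|---|---|---|
| 0 | 87.0% | 11.6% |
| 0.3 | 83.0% | 14.9% |
| 0.6 | 78.5% | 20.2% |
| 0.8 | 73.9% | 24.0% |

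Allowing for simulation error, the ranges are roughly 73–87% and 12–24%. The simulated values sit slightly below the formula for the any-of-three rule because a small group's percentage is above its complement a little less than half the time (48–49%).

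**5. Effect of an interval.** If a group counts as higher only when its unadjusted 95% lower limit is above zero, the chance that at least one of three does so with no true difference falls to about 7–9%. With a three-way correction it is about 3–4%.

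**The case against.** The strongest reply is that this is an exploratory endpoint in a pilot built for estimation. Sections 3.1, 3.3 and 3.4 say so, section 20.1 speaks only of what is anticipated, and section 20.4 only undertakes to characterize reach. On that view descriptive rates are enough. The pool wording in 20.3 could also be a slip that any analyst would put right, since Aim 5 covers moderation of treatment effects as well, and for that the randomized pool is correct.

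Much of this stands. A reader might infer that the plan will declare superiority whenever any named group shows a higher percentage, and so carries a false-claim rate near nine in ten. The documents do not support that. No section says a higher percentage is sufficient or that one group of three is enough, and 87.5% is the ceiling of the formula above, reached only with unrelated contrasts. A reader might also infer that a multiplicity-adjusted superiority test is required. For an exploratory pilot endpoint that is a choice, not a necessity.

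The reply does not remove the gap. Estimating a difference still calls for the difference and its uncertainty. Section 20.4 promises odds ratios, numbers needed to treat and effect sizes for the arm comparison but nothing comparable for reach. And the pool in 20.3, taken literally, makes the reach question unanswerable.

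**Conclusion.** The point holds as a gap in specification. The Aim 5 reach hypothesis has no contrast, no interval and no criterion, and its assigned population has no variation in reach. Primary endpoints and safety are unaffected.

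The pool conflict rests on the text alone. The half-widths and chance figures rest on the plan's 833 patients and 12% reach together with assumed subgroup shares and overlap. The chance figures also depend on a reading rule that is not the plan's. They show how little a bare percentage says and are not the error rate of a stated procedure. The intervals will be wide: 7.4 points either side on a 12% base for an 83-patient group. A reader of raw percentages would not see this.

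**What to change.** - **Section 20.3:** state that the Aim 5 reach analysis uses everyone on at least one CRDS report (the Aim 1 pool). Keep the randomized pool for moderation of treatment effects.
- **Section 20.4:** for each named group, report the reach difference and ratio against all other listed patients with a 95% confidence interval, labelled as exploratory estimation. Do not describe reach as superior where the interval includes no difference. An adjustment for three comparisons is optional.
- **Sections 3.3 and 20.1:** give the hypothesis one status, exploratory or secondary.
- **Denominator:** state it for neighborhood disadvantage. Section 5.1 keeps basic demographics and insurance type for patients who opt out but does not list a neighborhood measure, and active decliners are left out of the further record extraction. If those patients drop out of this comparison, say so, because removing people who mostly did not start treatment raises apparent reach.

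The cost is a few sentences and a short table. Race and insurance type are already collected; the neighborhood measure needs the denominator statement above. The downside is that a small favourable gap can no longer be reported as superior reach.

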For Aim 3, we hypothesize that the majority of patients assigned to each condition will initiate treatment and will receive at least some counseling and use at least some of the provided medication. We also hypothesize that patient ratings of acceptability and satisfaction will be favorable. We also expect retention, adherence, and satisfaction with treatment to be higher in enhanced care relative to the standard care control condition. We anticipate that the more-intensive treatment, although more costly, will be cost-effective in terms of the incremental cost effectiveness ratio per additional

PROTOCOL TITLE: Comparative Effectiveness Trial of Tobacco Cessation Treatments among Cancer Patients who Smoke

patient who quits smoking, relative to the comparator condition and to other preventive health interventions.

For Aim 4, we are not testing a specific hypothesis. Instead, we are seeking patient input to enhance the acceptability of tobacco treatment outreach and the relevance of smoking cessation counseling for participants in the CET.

For Aim 5, we expect treatment reach to be especially high among historically undertreated populations (including African-American, Medicaid-eligible patients, and those from disadvantaged neighborhoods), and for the effects of enhanced care (vs. the standard care comparator) to be similar across patient subgroups.

3.4 Study endpoints.

Primary endpoints:

1. Reach of smoking treatment, defined as the proportion of eligible patients who initiate evidence-based smoking treatment through the opt-out referral program. (Aim 1)
2. Biochemically verified 7-day point-prevalence abstinence 26 weeks after a target quit date (confirmed by expired carbon monoxide and/or a cotinine urine or saliva sample test). (Aim 2)

Secondary endpoint:

1. Self-reported 7-day point-prevalence abstinence 12 weeks after a target quit date. (Aim 2).

Exploratory endpoints:

1. Treatment acceptability and feasibility indicators including treatment retention (at each treatment contact/milestone) and completion, medication adherence, patient satisfaction, and patient ratings of burden. (Aim 3).
2. Treatment costs from payer and patient perspectives. (Aim 3).
3. Incremental cost-effectiveness ratios for each additional patient who quits smoking with higher-intensity treatment versus lower-intensity treatment. (Aim 4).

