4.3 **Criteria for considering participants “enrolled.”** Individuals will be considered enrolled in the study at the point of randomization to a study arm in the CET. Randomization will occur after oral consent to participate and completion of baseline assessments. People who do not complete oral consent and randomization will not be considered fully enrolled and will be replaced until 50 people are randomized in the CET (25 in each arm).

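### Equivalent effectiveness across patient groups is a stated hypothesis with no margin, method or reading rule, and 50 patients can neither support nor refute it

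*Combined protocol and SAP*

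**What the plan says.** Section 20.1 (Statistical Hypotheses) places Aim 5 under secondary hypotheses and closes it by anticipating superior reach among underserved groups and "equivalent effectiveness across patient groups". Section 3.3 puts the Aim 5 hypothesis under exploratory hypotheses and words it as an expectation "for the effects of enhanced care (vs. the standard care comparator) to be similar across patient subgroups".

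Section 20.4 gives the method: "Logistic regression will be used to estimate the effects of treatment condition on binary outcome data", with effects examined "overall and by patient subgroups (i.e., moderation effects"). Odds ratios and numbers needed to treat are the effect measures. No interaction test, significance level, equivalence margin or confidence-interval rule is named.

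Two passages link these results to equity. Section 3.1 includes subgroup differences in comparative effect as the way to assess equity of outcomes. The intervention row of the Section 1.0 summary says the comparison, including abstinence across subpopulations, is meant to identify the most effective, efficient and equitable treatment.

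On size, Section 4.3 plans that "50 people are randomized in the CET (25 in each arm"). Section 20.2 concedes limited sensitivity ("A sample of 50, while too small to sensitively test for moderate treatment benefits") and describes the subgroup work as exploration.

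**The concern.** Equivalence has a technical meaning in a section on statistical hypotheses, and Section 20.1 appears to use it that way. It labels the Aim 2 comparison and the Aim 3 hypotheses as superiority, gives null hypotheses for Aim 3, and then sets superior reach against equivalent effectiveness for Aim 5. An equivalence hypothesis needs a margin and an analysis that can exclude differences larger than it. Neither is given.

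What remains is a moderation analysis. In a trial of this size, failing to detect moderation is the expected outcome whether or not effects differ, so that outcome would match the hypothesis while carrying almost no information. Equity is one of the three dimensions on which the treatments are to be compared, and the pilot is meant to inform a full-scale trial. An unsupported impression of equal benefit could therefore carry forward. The difference in status (secondary in 20.1, exploratory in 3.3) leaves the weight of the hypothesis unclear.

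**Working it through.** The documents attach no power or precision figure to the sample of 50, so there is no planned figure to reproduce. The check asks how precisely 50 patients can estimate a difference in treatment effect between two subgroups.

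**Inputs from the documents**
- 25 randomized per arm (Section 4.3); all randomized patients are analysed, with missing counted as smoking (Sections 20.2, 20.3).
- Abstinence 34.5% vs 21.5%, from the trial in cancer patients cited in Section 2.5. The odds ratio is (0.345/0.655)/(0.215/0.785) = 1.92.
- Predicted odds ratio of at least 1.50 (Section 20.1), used as an alternative.
- Nine listed moderators (Aim 5): age, race, sex, ethnicity, socioeconomic disadvantage, nicotine dependence, cancer site, stage and treatment phase.

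**Assumptions not in the documents**
- The cited rates apply in both subgroups.
- Subgroup share of 50%, with 20% and 10% as alternatives.
- Two-sided 5% for any test; 5% per side for equivalence.
- Equivalence margins of 1.5-, 2- and 3-fold on the ratio of odds ratios.

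**Precision**

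SE of the log ratio of odds ratios = sqrt(sum over the four arm-by-subgroup cells of 1/(n p (1 − p))).

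Equal halves, n = 12.5 per cell:
- Within one half: 1/(12.5 × 0.345 × 0.655) + 1/(12.5 × 0.215 × 0.785) = 0.354 + 0.474 = 0.828.
- Both halves: 2 × 0.828 = 1.656, so SE = 1.29.
- 95% factor: exp(1.96 × 1.287) = 12.5. An observed ratio of exactly 1.0 would have an interval of about 0.08 to 12.5.
- 90% factor, which two one-sided 5% tests would use: exp(1.645 × 1.287) = 8.3. Even a perfect estimate of 1.0 could not meet a margin tighter than about 8.3-fold.

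| Smaller subgroup's share | SE | 95% factor |
|---|---|---|
| 50% | 1.29 | 12.5 |
| 20% | 1.61 | 23 |
| 10% | 2.14 | 67 |

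Using the predicted odds ratio of 1.50 with a 21.5% control rate (29.1% in the enhanced arm) gives a factor of 13.1 for equal halves, so the result does not depend on which planning effect is chosen.

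**If an interaction were tested at 5%**

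For equal halves, approximate power is 8%, 14% and 24% for a true ratio of odds ratios of 2, 3 and 5. In 40,000 simulated trials (0.5 added to each cell count), with an odds ratio of 2.94 (the primary care trial in Section 2.4) in one half and 1.0 in the other, the interaction was significant in 9%. With the odds ratio of 1.0 in a 20% subgroup it was significant in 5%, and 51% of trials had at least one cell with no abstainers or only abstainers.

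**Size needed to show equivalence**

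N per arm = V × (1.645 + 1.282)² / (ln margin)², for 80% power and a true ratio of 1. V is the squared SE for one patient per arm; for equal halves, V = 25 × 1.656 = 41.4.
- 3-fold margin: 41.4 × 8.564 / 1.207 = 294 per arm, 588 in total.
- 2-fold margin: 738 per arm, 1,476 in total.
- 1.5-fold margin: 2,157 per arm, 4,314 in total.

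The plan has 50 in total.

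**The case against.** The best defence is that this is a pilot stating an expectation. Both sections use the language of expecting or anticipating, and neither says the trial will demonstrate equivalence. Aim 5 is framed as estimating how far effects differ, Section 20.4 speaks of estimating, and Section 20.2 admits that 50 is small. A pilot may state an expectation that it is not sized to confirm.

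Much of this stands, and it rules out two stronger readings. A reader might infer that an interaction test is the planned test of the hypothesis. The documents do not support that: Section 20.4 names no test, significance level or p-value rule. For an estimation plan the interval width is the relevant figure, and the power figures above are secondary. A reader might also infer that a null moderation result will be taken as proof of equity. No passage says so. Section 3.1 limits these endpoints to generating estimates and sample-size needs for a later trial, and Section 20.2 calls the subgroup work exploration.

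The defence does not remove the gap. The admission in Section 20.2 concerns treatment benefits, not similarity of effects, and the same section promises stable estimates. If subgroup work is exploratory, a secondary hypothesis of equivalence is inconsistent with it. Nothing in the text tells the analyst how to describe an absence of detected moderation.

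**Conclusion.** The concern holds in a limited form. Equivalence of effect across patient groups is hypothesised without a margin, method or interpretation rule, and its status differs between Sections 3.3 and 20.1. In the favourable case of a half/half split, the 95% confidence interval for a ratio of odds ratios spans the estimate multiplied and divided by about 12.5, so the data are compatible with very large differences in either direction. Absence of detected moderation would agree with the hypothesis uninformatively.

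The figures rest on the cited trial's rates holding in both subgroups and on an assumed subgroup share. Unequal shares widen the interval, and the predicted odds ratio of 1.50 changes it little. The primary abstinence analysis is unaffected. The matter concerns what the trial can claim about equity.

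**What to change.** - **Sections 3.3 and 20.1:** drop the equivalence hypothesis, or recast it as a descriptive, exploratory expectation. Give it the same status in both places.
- **Section 20.4:** report the subgroup contrast for each moderator, for example the ratio of odds ratios, with a 95% confidence interval. Show abstainer counts by arm and subgroup, because cells with no abstainers or only abstainers are likely in small subgroups.
- **Section 20.4, reading rule:** add a sentence such as: *Subgroup contrasts are exploratory; absence of detected moderation will not be described as similar, equivalent or equitable effectiveness.*

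A margin-based assessment, if wanted, belongs in the full-scale trial. These changes need no additional patients, data or procedures. The cost is a weaker stated claim about equity.
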